9.5.2 Analyses of Secondary Efficacy Endpoint(s)

For the secondary endpoints including change from baseline at week 16 in PPPASI total score, PPSI total score, subject's VAS assessment for PPP symptoms (pruritus and pain/discomfort), and DLQI total score, the MMRM with treatment group, visit time, treatment-by-time interaction, and stratification factors as fixed effect, and the baseline value as a covariate will be applied. An unstructured covariance matrix will be used to model the correlation among repeated measurements. For the treatment failures as the result of an IE (IP discontinuation prior to week 16 due to lack of efficacy, adverse event, or use of protocol prohibited medication), the corresponding endpoints' baseline value will be assigned to the data on and after the IE up to week 16, regardless of the observed data. The missing data due to other reasons will not be imputed considering MMRM application based on the assumption of MAR. The least square (LS) means and SEs along with 95%CI within-group and treatment differences (from placebo) in LS means and SEs along with 95%CI and two-sided p-values will be derived from the MMRM.

The secondary endpoints will be statistically tested in the following order if the primary analysis result achieve a statistically significant difference. The statistical testing will be performed in the sequence until one of the analyses has failed to show the statistically significant difference at a significance level of 0.05 (two-sided).

- 1. Change from baseline in PPPASI total score at week 16
- 2. Change from baseline in PPSI total score at week 16
- Change from baseline in Subject's VAS assessment for PPP symptom (pruritus) at week 16
- Change from baseline in Subject's VAS assessment for PPP symptom (pain/discomfort) at week 16
- 5. Change from baseline in DLQI total score at week 16

Endpoint/Estimand	Summary and Analysis Method				
 Change from baseline in PPPASI total score at week 16 Change from baseline in PPSI total score at week 16 Change from baseline in Subject's VAS assessment for PPP symptom (pruritus) at week 16 Change from baseline in Subject's VAS assessment for PPP symptom (pain/discomfort) at week 16 	 LS mean (SE) along with 95%Cl within-group derived from the MMRM LS mean difference from placebo (SE) along with 95%Cl and p-value (two-sided) based on the MMRM For the treatment failures, the corresponding endpoints' baseline value will be assigned to the data on and after the IE up to week 16, regardless of the observed data. The missing data due to other reasons will not be imputed considering the MMRM application based on the assumption of MAR. 				
 Change from baseline in DLQI total score at week 16 					
Sensitivity analysis will not be performed for the secondary efficacy endpoints.					

Table 9-2.	Secondary		/ Endpoint	Summar	v Table
	Occontaat	/ Lincacy		Guillina	y lable

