9.3.1 Covariates

Baseline value will be the covariate in the analysis model (eg, Mixed-effect Model for Repeated Measures [MMRM]) to derive within-group means and standard errors (SEs), treatment differences (from placebo) in means and SEs, and 95% CI.

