	be conducted at the 2-sided 0.05 significance level and the adjusted		
	treatment difference of the proportion of subjects achieving		
	PPPASI-50 response, using the weighted average of the treatment		
	differences across the strata, along with the associated 2-sided		
	95 % CIs will be provided.		
Secondary	The main estimand for the secondary efficacy endpoints is the		
	difference in change from baseline at week 16 in PPPASI total score,		
	PPSI total score, subject's VAS assessment for PPP symptoms		
	(pruritus and pain/discomfort), and DLQI total score based on the ITT		

Protocol Number: 20200195

Date: 15 April 2022 Page 55 of 99

population in which subjects who discontinue the IP due to lack of efficacy, adverse event, or use of protocol prohibited medication are considered as treatment failures.

- The target population of interest is Japanese subjects with PPP defined through the inclusion/exclusion criteria.
- The secondary endpoints are the change from baseline at week 16 in PPPASI total score, PPSI total score, subject's VAS assessment for PPP symptoms (pruritus and pain/discomfort), and DLQI total score.
- The IEs are IP discontinuation due to lack of efficacy, adverse event, or use of protocol prohibited medication. The baseline value will be assigned to the data after any of the IEs through week 16 regardless of the observed data.
- The summary measure is the mean difference in change from baseline.

For the continuous efficacy secondary endpoints including change from baseline at week 16 in PPPASI total score, PPSI total score, subject's VAS assessment for PPP symptoms (pruritus and pain/discomfort), and DLQI total score, the MMRM with treatment group, visit time, treatment-by-time interaction, and stratification factors as fixed effects, and the baseline value as a covariate will be applied. The data where the baseline value is assigned for the treatment failures will be used for the MMRM analyses based on the assumption of MAR. The least square (LS) means and standard errors (SEs) within-group and treatment differences (from placebo) in LS means, and SEs along with 95%CI and p-values will be derived from the MMRM.

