3.1 Study Design

This is a phase 3, multicenter, randomized, double-blind, placebo-controlled study evaluating the efficacy and safety of apremilast 30 mg BID versus placebo in Japanese subjects with PPP.

Approximately 170 subjects will be randomized in a 1:1 ratio to 1 of 2 treatment groups: apremilast 30 mg BID or placebo. Subject randomization will be stratified by a subject's rounded PPPASI total score ($\leq 20/21-30/ \geq 31$) and focal infection status (yes/no) at baseline.

Randomized subjects will receive either apremilast 30 mg BID or placebo for 16 weeks, the duration of the double-blind placebo-controlled treatment period. During the active treatment period (week 16 to week 52), all subjects will receive apremilast 30 mg BID. After the final dose treatment, subjects will enter a 30-day safety observational follow-up period. The total study duration including 4 weeks screening per subject is approximately 60 weeks.

The primary analysis will be performed after all subjects have either completed the week 16 visit (visit 8) or have discontinued the study. A supplemental analysis will be conducted after all subjects have either completed the week 24 visit (visit 10) or have discontinued the study. The final analysis will be conducted after all subjects have either completed the week 56 visit (visit 14) or discontinued the study.

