4.1 Planned Covariates

For the secondary endpoints to be analyzed with MMRM model (i.e., change from baseline at week 16 in PPPASI total score, PPSI total score, subject's VAS for PPP

symptoms [pruritus and pain/discomfort], DLQI total score), the corresponding baseline value of the endpoint will be included as a covariate in the model.

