9.5 Efficacy Analyses

The efficacy analyses will be performed based on the ITT population.

To control the overall type I error at the level of 0.05 (2-sided), a fixed-sequence testing procedure will be applied. The secondary efficacy endpoints will be tested with the listed order in Section 9.5.2 if the primary endpoint achieves statistical significance.

Sensitivity analyses will be performed for the primary estimand.

Subject data listings of efficacy data will be provided.

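### Optional: the secondary-endpoint MMRM has no baseline-by-visit term; the test is valid, but the week-16 PPPASI standard error may be about 0–6% larger than with the term

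*SAP*

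**What the plan says.** SAP 9.5.2 analyses the changes in PPPASI, PPSI, the two VAS scores and DLQI with "the MMRM with treatment group, visit time, treatment-by-time interaction, and stratification factors as fixed effect, and the baseline value as a covariate". On the covariance it states: "An unstructured covariance matrix will be used to model the correlation among repeated measurements". For treatment failures, the endpoint's "baseline value will be assigned to the data on and after the IE up to week 16"; other missing values are left to the model.

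SAP 4.1 gives the same role to baseline: "the corresponding baseline value of the endpoint will be included as a covariate in the model". The protocol agrees. Section 9.3.1 says "Baseline value will be the covariate in the analysis model", and 9.4.2.2 specifies "the MMRM with treatment group, visit time, treatment-by-time interaction, and stratification factors as fixed effects, and the baseline value as a covariate", as does the synopsis (1.1). No section lists an interaction of baseline, or of the stratification factors, with visit.

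Two other provisions matter here. On allocation, SAP 3.1 says: "Subject randomization will be stratified by a subject's rounded PPPASI total score" (three bands), with focal infection as the second factor. On multiplicity, SAP 9.5 says: "The secondary efficacy endpoints will be tested with the listed order in Section 9.5.2 if the primary endpoint achieves statistical significance". Change in PPPASI comes first in that order. SAP Table 9-2 plans no sensitivity analysis for the secondary endpoints.

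**The concern.** A main effect of baseline forces the same slope at every visit. For PPPASI this may not fit. The primary endpoint is a percentage reduction, and if improvement is roughly proportional to the starting score, the slope of absolute change on baseline is small at week 2 and steepens as the response develops. The PPPASI-band factor cannot absorb this, because it too has no visit interaction.

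The misfit then goes into the unstructured residual variance, and the week-16 standard error is larger than it need be. At stake is a little power for the first gated secondary test. If that test fails, the other four are not formally tested. The primary endpoint is unaffected.

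**Working it through.** **The plan's own figure.** The only power statement concerns the primary endpoint (SAP 3.2): 85 per arm, 40% vs 65%, two-sided 0.05, 90%. Power = Φ[(Δ√n − 1.96√(2p̄q̄)) / √(p₁q₁ + p₂q₂)] = Φ[(0.25√85 − 1.96×0.7062)/0.6837] = Φ(1.347) = 91.1%. With 81 per arm (5% loss) it is 89.7%. The stated 90% is reproduced. The documents give no power, SD or effect size for the MMRM endpoints, so the point has to be examined by simulation.

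**Mechanism.** Let s_t be the share of the week-16 effect reached at visit t and m the mean proportional improvement at week 16. The slope of change on baseline at visit t is about −s_t·m. A common slope β leaves (−s_t·m − β)(B − mean B) in the residual at visit t. With s = 20% at week 2 the first slope is one fifth of the last; with a flat course the slopes are equal and nothing is lost.

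**Inputs from the documents.** 170 subjects 1:1; the six strata; visits at weeks 2, 4, 6, 8, 12 and 16; PPPASI ≥ 12 at entry; 40% and 65% responders; 5% dropout.

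**Assumed inputs.** Baseline PPPASI mean 26, SD 9; focal infection 30%; SD of proportional improvement 0.35; adjacent-visit correlation 0.85; permuted blocks of 4; response rates applied before failures; the 5% treated as failures set to baseline from a random visit. Both models were fitted by REML with unstructured covariance and stratification factors, 10,000 trials per course.

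Ratios are planned model ÷ model with the term; percentages are planned vs with the term.

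| Course (share of effect by visit, %) | Reported SE ratio | Sampling-SD ratio | PPPASI power | Primary and PPPASI both succeed |
|---|---|---|---|---|
| Gradual 20/35/50/62/85/100 | 1.058 | 1.012 | 92.6 vs 94.2% | 85.2 vs 86.2% |
| Intermediate 35/52/66/77/92/100 | 1.032 | 1.006 | 93.3 vs 94.2% | 85.6 vs 86.2% |
| Early 50/72/85/92/100/100 | 1.016 | 1.003 | 93.7 vs 94.2% | 85.9 vs 86.2% |

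With equal slopes (5,000 trials) the SE ratio is 0.9996. The mean estimate in the central run is −5.01 vs −5.00.

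**Splitting the excess.** Reported SE ratio = (SE/SD, planned) ÷ (SE/SD, with term) × sampling-SD ratio.
- Gradual: 1.042 ÷ 0.997 × 1.012 = 1.058.
- Early: 1.010 ÷ 0.997 × 1.003 = 1.016.

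Most of the excess is therefore the planned SE lying above the estimator's true SD, because stratification already balances baseline. Under simple randomization, which is not the design, the gradual ratios are 1.055 reported and 1.052 true.

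**Validity.** With no treatment effect, rejection was 4.16% planned vs 5.00% with the term (gradual) and 4.68% vs 4.92% (early).

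**Dependence on the assumptions.**
- Baseline measurement error SD 4 (regression to the mean): 2.5%, 1.3% and 0.5% for the three courses.
- Grid of 3 courses × 3 baseline SDs × 3 correlations × 2 response SDs × 2 error levels = 108 settings, 800 trials each: reported excess median 1.3%, 90th percentile 5.0%, maximum about 14%; true precision loss median 0.3%, maximum 2.9%; gain in joint success median 0.1 points, maximum 3.9.
- A second set with other inputs (baseline mean 28, SD 8 or 11; correlation 0.7; 1,000 stratified trials each): 0.2% flat, 1.1–1.7% fast, 4.3–6.1% linear; estimates equal within 0.03 points; planned test rejecting 4.4–6.3% under the null (Monte Carlo error about ±1.4 points). Here the planned SE was at most 2% above its sampling SD, and the true precision loss for a linear course was 1.6–2.3%.
- Residual SD 0.25 with a linear course: roughly 9–13%, from only 40 trials.
- Improvement capped at 100% and residual SD growing with the course (2,000 trials): 3.3% gradual, 0.8% early.

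**The case against.** The strongest reply is that this is a preference. The protocol and SAP specify the same model, it can be run as written, it gives a valid test, and it leaves the primary endpoint alone. All of that stands.

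The second reply is that the size comes from assumptions. That stands too. The 1.6–5.8% of the central runs is not typical of the grid, whose median is 1.3%. The central runs also assume no baseline measurement error, although a minimum score at entry makes some regression to the mean plausible; allowing for it more than halves the figures.

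The third reply is that how the excess divides between conservatism and lost efficiency is not settled: the gradual runs put the planned SE 4.2% above its true SD, while the second set gives at most 2%. This is fair, and it is a reason not to lean on exact type I error figures.

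None of this removes the point. With slopes that steepen, the direction was the same in every set of runs, and the term costs almost nothing when the slopes are equal.

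**Conclusion.** The point holds as an optional improvement. Under assumed inputs, the reported week-16 SE for PPPASI change is about 0–6% larger than with a baseline-by-visit term (grid median 1.3%; larger if residual variance is small). The true precision gain is about 0–1% in the central runs. Power for the PPPASI test alone rises by about 0.5–1.6 points there, and the probability that both tests succeed by 0.3–1.0 points.

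Three stronger readings are tempting and not supported:
- *That the planned test is biased or invalid.* The estimates agree and rejection under the null is at or slightly below 5%, within simulation error.
- *That the SE is overstated, or precision lost, by the whole 1.6–5.8%.* That figure compares two models. Against the planned estimator's own sampling SD, the excess in the same runs is 1.0% (early) to 4.2% (gradual).
- *That similar figures apply to PPSI, VAS or DLQI.* The documents give nothing from which to set inputs for them, so no numerical claim is made.

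**What to change.** Before the week-16 database lock, add a baseline-by-visit interaction to the MMRM in SAP 9.5.2 and Table 9-2, keeping all other terms and the unstructured covariance. Align SAP 4.1, and record the departure from protocol 1.1, 9.3.1 and 9.4.2.2 in SAP Section 10. After the lock, the extended model could serve only as a supportive analysis.

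The cost is five extra parameters for endpoints with six post-baseline visits and one for DLQI (weeks 8 and 16 only). No new data are needed. If the slopes are in fact equal, the SE is up to about 0.3% larger. This agrees with the loss of about one degree of freedom at week 16: 170 subjects less 6 parameters (intercept, treatment, two band contrasts, focal infection, baseline) leaves 164, and √(1 + 1/164) ≈ 1.003.

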9.5.3 Analyses of Exploratory Efficacy Endpoint(s)

 Table 9-3. Exploratory Efficacy Endpoint Summary Table

Endpoint	Summary and Analysis Method

Endpoint	Summary and Analysis Method

9.6 Safety Analyses

Safety analyses will be performed using the safety analysis population unless otherwise specified. Summaries of the safety analyses for the placebo-controlled period will be based on the safety population and presented by treatment group, and the safety analyses for the apremilast-exposure period will be based on the apremilast subjects as treated population and presented by treatment group (Placebo/30 mg BID, 30 mg BID as initiated and 30 mg BID as treated). The purpose of safety summary for the apremilast-exposure period will be based on g BID.

9.6.1 Analyses of Primary Safety Endpoint(s)

There is no primary safety endpoint. As a secondary endpoint, the safety and tolerability of apremilast 30 mg BID will be compared to placebo. No inferential testing for statistical significance will be performed for safety analyses.

Unless otherwise specified, the analyses of AEs and marked abnormalities (laboratory parameters and vital signs) for both the placebo-controlled period and apremilast-exposure period will be summarized by subject incidence rate. For safety summaries of apremilast-exposure period, the exposure-adjusted incidence rate will be presented to account for the difference exposure to the IP.

9.6.2 Adverse Events

Adverse events will be analyzed in terms of treatment-emergent adverse events (TEAEs) defined as any AEs that begin or worsen on or after the first dose of IP through 30 days after the last dose of IP or study treatment discontinuation date, whichever is later. The Medical Dictionary for Regulatory Activities (MedDRA) version 24.0 or higher will be used to code all events categorized as adverse events to a system organ class and a preferred term.

An **overview** of the following AE categories will be provided.

AE Categories:

- TEAE
- Drug-related TEAE
- Severe TEAE
- Serious TEAE
- Serious Drug-related TEAE
- TEAE Leading to Drug Interruption
- TEAE Leading to Drug Withdrawal
- TEAE Leading to Death

Summary of the above AE categories for the subgroups in Section 4.2 will be provided.

Tables summarizing the incidence of TEAEs by SOC and/or PT will be generated for each of the followings:

- All TEAEs
- Drug-related TEAE
- TEAEs by maximum severity
- Serious TEAE
- Serious Drug-related TEAE
- TEAE Leading to Drug Interruption
- TEAE Leading to Drug Withdrawal
- TEAE Leading to Death
- First onset and new event of TEAE by exposure interval
 - Placebo controlled period (weeks): ≤ 1, > 1 to ≤ 2, > 2 to ≤ 4, > 4 to ≤ 8, > 8 to ≤ 12, > 12 to ≤ 16, > 16
 - Apremilast-exposure period (weeks): ≤ 1, > 1 to ≤ 2, > 2 to ≤ 4, > 4 to ≤ 8, > 8 to
 ≤ 12, > 12 to ≤ 16, > 16 to ≤ 28, > 28 to ≤ 40, > 40 to ≤ 52, > 52
- TEAE for the subgroups in Section 4.2

Tables summarizing the incidence of TEAEs by PT will be generated for each of the followings:

- TEAEs by NSAIDs status
- Most frequent TEAEs (subject incidence ≥ 5% in any group or another cut-off if justified)
- Most frequent TEAEs by maximum severity (subject incidence ≥ 5% in any group or another cut-off if justified)
- Most frequent TEAE for the subgroups in Section 4.2 (subject incidence ≥ 5% in any group or another cut-off if justified)
- First onset of most frequent TEAE by exposure interval (subject incidence ≥ 5% in any group or another cut-off if justified)
 - Placebo controlled period (weeks): ≤ 1, > 1 to ≤ 2, > 2 to ≤ 4, > 4 to ≤ 8, > 8 to ≤ 12, > 12 to ≤ 16, > 16
 - Apremilast-exposure period (weeks): ≤ 1, > 1 to ≤ 2, > 2 to ≤ 4, > 4 to ≤ 8, > 8 to
 ≤ 12, > 12 to ≤ 16, > 16 to ≤ 28, > 28 to ≤ 40, > 40 to ≤ 52, > 52

For the summary of the new events of TEAE by exposure interval, each subject is counted once for either subject incidence or EAIR for each applicable specific TEAE in each exposure interval where an event started. The denominator of a subject incidence is the number of subjects with exposure time exceeding the lower bound of the particular exposure interval, while the denominator of an EAIR is the sum of the exposure time during the exposure interval (up to the first event start date for subjects with at least one event starting in the interval) among the same number of subjects as in the denominator of the corresponding subject incidence. The exposure time for a subject without the specific event is the treatment duration, whereas the exposure time for a subject with the specific event is the treatment duration up to the start date (inclusive) of the first occurrence of the specific event. For the summary of the first onset of TEAE by exposure interval, only the first onset of specific TEAE is considered for each subject.

Following TEAEs of interest will be summarized according to their categories and PT by severity (mild, moderate, severe), relationship, action taken with IP, fatality, and seriousness.

- Depression: MedDRA narrow scope SMQ of Depression (excluding suicide and self-injury)
- Serious infection: MedDRA primary SOC of Infections and infestations and the events assessed as serious
- Risk of Triggering Suicide: MedDRA narrow scope sub-SMQ of Suicide/selfinjury
- Serious Diarrhea, Nausea, and Vomiting: definition can be found in TFLSD.
- Malignancies: definition can be found in TFLSD.
- Vasculitis and Vasculopathy: MedDRA narrow scope SMQ of Vasculitis.
- Serious Hypersensitivity: MedDRA narrow scope SMQ of Hypersensitivity.
- Weight Change (Weight decrease): definition can be found in TFLSD.

Subject listings of AEs including non-treatment-emergent AEs will be provided.

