8.4.4.1 Time Period and Frequency for Collecting and Reporting Safety Event Information

8.4.4.1.1 Adverse Events

The adverse event grading scale to be used for this study will be the Amgen Standard Grading Scale and is described in Section 11.4.

The investigator is responsible for ensuring that all adverse events observed by the investigator or reported by the subject that occur after first dose of investigational product through the end of study are reported using the Events CRF.

Protocol Number: 20200195

Date: 15 April 2022 Page 48 of 99

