5.1 Safety Related Definitions

5.1.1 Treatment-emergent Adverse Events (TEAEs)

Any AEs that begin or worsen on or after the first dose of IP through 30 days after the last dose of IP or study treatment discontinuation date, whichever is later.

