5.2.2 End of IP Admin Date

End of IP Admin for each subject is defined as the date the decision was made to end IP as recorded on the End of IP CRF page.

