5.5 Analysis Phases

• Placebo-controlled Phase/Period – Weeks 0 to16

This period starts on the day of randomization (Week 0/Visit 2), and stops on below:

(1) the day of Week 16/Visit 8 if the subject continued study treatment to the active treatment phase

(2) the day of the discontinuation if the subject discontinued study treatment prior to or at Week 16/Visit 8

(3) the last known study day if the subject is lost to follow-up prior to or at Week 16/Visit 8

• Active Treatment Phase/Period – Weeks 16 to 52

This period starts on one day after the day of the dose of apremilast distributed at Week 16/Visit 8, and stops on either below.

(1) the day of Week 52/Visit 13

(2) the day of the discontinuation if the subject discontinued prior to or at Week 52/Visit13

(3) the last known study day if the subject lost to follow-up prior to or at Week 52/Visit 13 during the phase

For safety analysis, the period starts on the day of the first dose of apremilast in the period.

• Safety Follow-up Phase/Period

Subjects who complete or discontinue the study treatment, will be followed up for 30 days after the end of treatment visit.

For adverse event analysis, data from the first 30 days after the last dose of IP will be included in the precedent treatment phase and data after the 30 days will be presented separately.

• Apremilast exposure period

This period starts on the date of either:

- the first dose of IP following randomization (Week 0/Visit 2) for subject who are treated with apremilast from Week 0

- the first dose of IP from the IP dispensed at Week 16/Visit 8 for subjects who were originally treated with placebo and are switched to apremilast at Week 16

This period stops on either: (1) data restriction date; or (2) the end of the study.

During the apremilast-exposure period, data are presented by treatment sequence, i.e., Placebo/30 mg BID, 30 mg BID as Initiated, and a total column of 30 mg BID as Treated.

6. Populations for Analysis

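### SAP 9.6.2: exposure-adjusted incidence rates count adverse events starting up to at least 30 days after last dose, but person-time stops at last dose

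*SAP*

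**What the plan says.** **Where EAIR is used.** SAP 9.6.1: "For safety summaries of apremilast-exposure period, the exposure-adjusted incidence rate will be presented to account for the difference exposure to the IP".

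**Which events count.** SAP 5.1.1 defines treatment-emergent events as "Any AEs that begin or worsen on or after the first dose of IP through 30 days after the last dose of IP". SAP 9.6.2 gives the full window: "through 30 days after the last dose of IP or study treatment discontinuation date, whichever is later". The discontinuation date may differ from last dose, since SAP 5.2.2 dates end of treatment as "the date the decision was made to end IP as recorded on the End of IP CRF page". On either parsing the window reaches at least 30 days past last dose. SAP 5.5 agrees: "data from the first 30 days after the last dose of IP will be included in the precedent treatment phase". The apremilast-exposure period itself ends only at the data restriction date or the end of the study. Post-dose events will be in the database, because protocol 8.4.4.1.1 requires that adverse events that "occur after first dose of investigational product through the end of study are reported using the Events CRF".

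**Which time counts.** SAP 9.6.2: "The exposure time for a subject without the specific event is the treatment duration". For a subject with the event, time ends at its first occurrence. SAP 5.2.8 ends treatment duration at the last dose date, and SAP 9.6.6 does the same for the apremilast-exposure period.

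**Interval tables.** In the new-event table a subject counts in every interval where an event begins, and belongs to the denominator if exposure time exceeds the interval's lower bound. One clause stops time at the first event within the interval. A later sentence stops exposure time at the first occurrence overall and does not say which table it serves.

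**The concern.** A rate needs its events and its time at risk to come from the same window. Here subjects can enter the numerator on days when nobody adds person-time.

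The purpose of EAIR in this SAP is to make columns with unequal apremilast exposure comparable: 52 weeks for subjects who start on apremilast and 36 weeks for those who switch at week 16. A fixed 30-day tail is a larger share of the shorter exposure, so the mismatch leans more on the switched column and works slightly against that purpose.

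In the interval tables the same mismatch can put a subject in an interval's numerator and outside its denominator. The SAP does not say how an event after last dose is assigned to an interval, so two programmers could produce different tables from the same data.

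**Working it through.** The documents state no EAIR, event count or post-dose event rate, so there is no figure to reproduce. The event rates and post-dose ratios below are assumptions, shown as ranges.

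**Inputs.** Planned apremilast treatment is T = 364 days (52 weeks, as initiated) or 252 days (36 weeks, switched), from SAP 3.1. The tail is 30 days (SAP 5.1.1). There are 85 subjects per arm (SAP 3.2); 81 switchers is 85 less the anticipated 5% dropout, rounded.

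**Model.** First events occur at rate L per day to last dose, then at r × L for 30 days, and everyone is treated for T days. Expected first events per subject are 1 − exp(−L(T + 30r)). Person-time per subject is [1 − exp(−LT)]/L. Dividing the rate by L gives

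ratio to on-drug rate = [1 − exp(−L(T + 30r))] / [1 − exp(−LT)]

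For rare events and r = 1 the excess tends to 30/T: 30/364 = 8.2% and 30/252 = 11.9%.

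**Results at 0.5 first events per person-year (L = 0.5/365.25).**

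| Post-dose rate | As initiated | Switched |
|---|---|---|
| equal (r = 1) | 0.4169/0.3924 = 1.062 | 0.3203/0.2918 = 1.098 |
| half (r = 0.5) | 1.031 | 1.049 |
| quarter (r = 0.25) | 0.3986/0.3924 = 1.016 | 0.2990/0.2918 = 1.025 |
| none (r = 0) | 1.000 | 1.000 |

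In subjects, with no further dropout and r = 1: 85 × 0.3924 = 33.4 plus 2.1 extra, and 81 × 0.2918 = 23.6 plus 2.3 extra. At r = 0.25 the extras are 0.5 and 0.6.

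**Rarer events.** At 0.05 per person-year and r = 1 the ratios are 1.080 and 1.117, but only about 0.3 extra subjects per column.

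**Between-column distortion at 0.5 per person-year.** 1.0977/1.0623 = 1.033 at r = 1, and 1.009 at r = 0.25.

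**Early-onset events.** Protocol 2.3 says most of the common events began in the first 2 weeks. Assume 20% of subjects have onset within 14 days, and the rest a rate of 0.1 per person-year. The ratio is then [0.2 + 0.8(1 − exp(−L(T − 14 + 30r)))] / [0.2 + 0.8(1 − exp(−L(T − 14)))]. At r = 1 this gives 0.2790/0.2731 = 1.022 and 0.2566/0.2505 = 1.024. At r = 0.25 it gives 1.005 and 1.006.

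**Interval example.** Count days from first apremilast dose. Last dose is on day 70 and an event starts on day 90. It is treatment-emergent, because 90 ≤ 70 + 30. By onset date it falls in the >12 to ≤16 week interval (after day 84, to day 112). Exposure of 70 days does not exceed 84, so the subject is in the numerator and adds no person-days.

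**Truncation example.** A subject is treated for 364 days with events on days 5 and 25; take the interval >2 to ≤4 weeks. Under the within-interval clause the subject is in the denominator with 25 − 14 = 11 days. Under first-occurrence truncation, exposure is 5 days, which does not exceed 14, so the subject leaves the denominator although the day-25 event is still counted.

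**Adding the tail to person-time.** With post-dose time to the first event or 30 days added to the denominator, the rate relative to L is [1 − exp(−L(T + 30r))] / {[1 − exp(−LT)] + exp(−LT)[1 − exp(−30rL)]/r}. At 0.5 per person-year and r = 0.25 this is 4.5% (as initiated) and 6.8% (switched) below the on-drug rate.

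**The case against.** **It may be a deliberate convention.** Dividing all treatment-emergent events by on-drug time can be a chosen approach. Each definition is stated openly, the overall rate can be computed as written, and the error can only overstate the event rate. That much stands. But the SAP does not declare such a convention, and it gives adjustment for exposure as the reason for using EAIR.

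**The effect is small and rests on assumed rates.** This stands in full and sets the priority.

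**Programming safeguards.** SAP 8.7 calls for validated macros and output checks, and 9.6.2 leaves some definitions to the table-shell document, which is not available here. Verification shows that a program follows its specification. It does not settle what the specification should be.

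**Stronger readings that the documents do not support:**
- A reader might take 8.2% and 11.9% as minimum unmatched time for everyone. They fit completers at the final analysis. Subjects still on treatment at the week 24 data cut have no tail, and someone who leaves the study early need not contribute 30 days, although for an early discontinuer who does, 30/T is larger.
- A reader might infer large errors in the interval rates. For >28 to ≤40 weeks in the switched column at 0.5 per person-year, [1 − exp(−L(56 + 28r))]/[1 − exp(−56L)] gives +12% (r = 0.25) to +47% (r = 1). That assumes mapping by onset date and takes the worst column. With 85 and 81 completers, the pooled as-treated column gives +4.7% to +18.5%. If only onsets within counted exposure enter an interval, the error is nil.
- A reader might conclude that the new-event table loses repeat-event subjects from its denominators. The within-interval clause is introduced for that table and would be redundant if first-occurrence truncation also applied, so the text discourages this reading. Only the scope of the later sentence needs stating.

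**Conclusion.** The mismatch is real on the text: the numerator runs past last dose, the denominator does not, and no section reconciles them. As an on-drug rate, EAIR is too high whenever a first event starts after last dose, and is unaffected otherwise.

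Under the constant-rate scenario for completers at the final analysis, the excess runs from zero to about 6% (52 weeks) and 10% (36 weeks), depending on the unknown post-dose rate. Early-onset events are affected by at most about 2.4% in the scenario shown. The interval tables are affected only if post-dose events are placed by onset date.

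This is a cheap improvement of low priority. SAP 9.6.1 says "No inferential testing for statistical significance will be performed for safety analyses", EAIR is presented for the apremilast-exposure period and not for the placebo comparison, and overall crude incidence and every efficacy result are untouched.

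**What to change.** In SAP 9.6.2:

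1. Base EAIR and its interval tables on events that begin or worsen from the first through the last apremilast dose date, over treatment duration.
2. Show treatment-emergent events starting after last dose in a separate table. They stay in crude incidence.
3. Require every subject in an interval's numerator to be in that interval's denominator.
4. As a minor clarification, state that within-interval truncation governs the new-event table, and first-occurrence truncation governs the first-onset table and the overall EAIR.

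Extending person-time by the tail is not recommended. It mixes off-drug time into the rate and, at a quarter post-dose rate, moves it further from the on-drug rate (−4.5%/−6.8%) than the present rule does (+1.6%/+2.5%).

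**Cost.** SAP wording and one derived variable from data already collected. EAIR and crude incidence will then use different event sets, which the tables must say, and comparison with summaries that use another denominator needs a footnote.
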